## E. PROTECTION OF HUMAN SUBJECTS

### Human Subjects Involvement, Characteristics and Design

Volunteers recruited for this study (N= up to 380) will be current smokers from the state of Texas area and/or Houston metropolitan community, who respond to media announcements related to the study (see Appendix AA). The Tobacco Research and Treatment Program's web screener database for tobacco users, outlined in IRB-approved PA18-0423, also may be used as a recruitment source for this study. This database houses data collected from an internet-based screening questionnaire to recruit tobacco users from the Houston area, as well as across Texas more broadly, who may be interested in participating in tobacco use and cessation studies at MD Anderson Cancer Center. PA18-0423 allows the sharing of data with IRB approved MD Anderson protocols. The Houston population is estimated at over 4 million with an ethnic distribution of 59% Caucasian, 19% African-American, 5% Asian, and 0.4% Native American, with 33% Hispanic or Latino (of any race) [157].

As shown in **Table 3**, inclusion criteria will include signing consent and agreeing to all study procedures, being between the ages of 21 and 65, having a working telephone and address where they may be reached, being interested in trying novel nicotine products, able to follow verbal and written instructions in English, and be the only participant in their household. Individuals will be excluded if they are unwilling to refrain from other e-cigarette use for the duration of the study, other than what is provided to them for study purposes, have had a bronchial or respiratory infection within the past 14 days, a spirometry FEV1 percentage reading is <50 (severe to very severe), have unstable medical conditions as determined by the medical team, abnormal heart rhythms or cardiovascular disease (stroke, chest pain, heart attack) in the last 3 months, meets criteria for Major Depressive Syndrome or suicidality on the PHQ-9, self-report of past or current diagnosis of bipolar disorder or schizophrenia/schizoaffective disorder, report use of tobacco products other than cigarettes or little cigars on 10 or more days in the last month, report recent (past 90 days), current, or planned (within the next 45 days) involvement in smoking cessation activities, or have a positive urine pregnancy test at screening.

Women who are one-year post-menopausal, or who have had a tubal ligation or a partial or full hysterectomy will not be subject to a urine pregnancy test. Also excluded are women who are pregnant, breastfeeding or of childbearing potential and not protected by a medically acceptable, effective method of birth control while enrolled in the study. Medically acceptable contraceptives include: (1) approved hormonal contraceptives (such as birth control pills, patches, implants or injections), (2) barrier methods (such as condom or diaphragm) used with a spermicide, or (3) an intrauterine device (IUD). Contraceptives sold for emergency use after unprotected sex are not acceptable methods for routine use. Also excluded are participants considered by the investigator to be unsuitable to participate in the study (e.g., due to cognitive deficits or instability to last the entire duration of the study). Daily smokers must report smoking 1 or more cigarettes per day (CPD). Intermittent smokers must report smoking 4 to 27 days per month, but will not be required to meet any minimum for CPD or expired CO, following the practice of Shiffman and colleagues [8].

**Table 3:** Inclusion Exclusion Criteria.

**Inclusion Criteria:**

- Sign consent and agree to all study procedures
- Age: 21-65 years old
- Have an address where he/she can receive mail
- Have a device available to conduct telehealth visit (e.g., smartphone, computer, tablet, internet access etc.) - Able to follow verbal and written instructions in English
- Willing and able to complete two spirometry sessions (this criterion waived during COVID-19 pandemic)
- Be the only participant in their household
- Interested in trying novel nicotine products
- Daily Smokers:  $\geq 1$  cigarette/little cigar per day
- Intermittent Smokers:  $\geq 1$  cigarette/little cigar per day 4 to 27 days per month
- Agrees to comply with all MD Anderson institutional policies related to COVID-19 screening prior to each in-person research visit.
- The individual agrees to not engage in study procedures or interactions with study personnel while operating a vehicle.

**Exclusion Criteria:**

- Unwilling to refrain from other e-cigarette use for the duration of the study, other than what is provided to them for study purposes.
- Current/recent use of certain medications:
  - a. Smoking cessation meds (past 90 days; e.g., Wellbutrin, Bupropion, Zyban, NRT, Chantix)
  - b. Certain medications to treat depression (last 14 days; e.g., Amitriptyline)
  - c. A case by case determination will be made by study physician for medication on the precautionary list (e.g., nitroglycerin)
  - d. self-reported daily use of opioids for 30 days or more on phone screen or at screening is exclusionary however PRN use is allowed (e.g., 3 to 7 days per week or less or if more frequent, use less than a month's duration.)
- Unstable medical condition as determined by the medical team
- Self-reported bronchial or respiratory infection in the last 14 days (this criterion waived during COVID-19 pandemic)
- Subject's spirometry FEV1 percentage reading is  $<50$  (severe to very severe obstruction) (this criterion waived during COVID-19 pandemic)
- Self-reported abnormal heart rhythms or cardiovascular disease (stroke, chest pain, heart attack) in the last 3 months
- Meets criteria for Major Depressive Syndrome or suicidality on the PHQ-9
- Self report of past or current diagnosis of bi-polar disorder or schizophrenia/ schizoaffective disorder
- Self-reported other tobacco use besides cigarettes or little cigars (e.g., hookah, cigarillos, smokeless tobacco, chewing tobacco, pipes, cigars, etc.) on 10 or more days in the last month.
- Recent (past 90 days), current, or planned (within the next 45 days) involvement in smoking cessation activities
- Positive urine pregnancy test at screening. Women who are one year post-menopausal, or who have had a tubal ligation or a partial or full hysterectomy will not be subject to a urine pregnancy test.
- Women that are breastfeeding or of childbearing potential and not protected by a medically acceptable, effective method of birth control while enrolled in the study. Medically acceptable contraceptives include: (1) approved hormonal contraceptives (such as birth control pills, patches, implants or injections), (2) barrier methods (such as condom or diaphragm) used with a spermicide, or (3) an intrauterine device (IUD). Contraceptives sold for emergency use after unprotected sex are not acceptable methods for routine use
- Subject considered by the investigator to be unsuitable to participate in the study (e.g., due to cognitive deficits or instability).

Note: For the purpose of eligibility requirements and ongoing smoking status, "cigarettes" will also include the tobacco product that is commonly known as "little cigars". Little cigars are machine-manufactured and sold in packs similar to cigarettes. They are often smoked by individuals of limited means because they are cheaper than conventional cigarettes.

All smokers will be prescreened by telephone for basic eligibility requirements (see Appendices P & CC). An initial description of the study design will be provided and data will be obtained on age, smoking history, other tobacco use, medical and psychiatric history, medication use, and pregnancy/lactation status. All participants who are initially eligible will be informed that they may be sent an email with a currently approved informed consent document for their review, an information slideshow (see Appendix BB.), and a questionnaire consent statement, and that, should they consent, they will be automatically connected to questionnaires hosted on MD Anderson's Qualtrics platform, prior to their scheduled baseline laboratory session. Participants will receive a phone call, email, and/or text message before their laboratory sessions to remind them of the appointment. Eligible participants will be scheduled for an in-person screening and may be emailed or mailed a confirmation letter and parking directions (see Appendix G). Given the nature of the study design it will be necessary to eliminate subjects who do not speak English or have a telephone.

**COVID-19 adaptation:** Spirometry-related inclusion and exclusion criteria will be waived until normal in-clinic operations are resumed and research-related spirometry is deemed safe to perform by the institution. Participants able to become pregnant will be mailed and asked to complete a pregnancy test at the virtual baseline screening and at Phases 1-4. Participants will be provided instructions for conducting the pregnancy test(s) at home (see Appendix AAA). Participants also will be asked to take a picture of the tests' results and to electronically send the picture to study staff through text or email.

**Informed Consent.** At the baseline session, the study purpose, other study requirements, and side effects will be reviewed including information related to the study's certificate of confidentiality (see Appendix OO). The information presented may come in the form of a slideshow (either paper or electronic) which will be developed in collaboration with the PI or Co-PI and will be based in part on current studies using VLNCC and/or directly from the informed consent document itself. Participants will be given the opportunity to ask questions about the informed consent document or any aspect of the study. Any medical questions that arise during the

process, if not addressed in the documentation or discussion provided, will be referred to the medical staff and the information will be provided to the potential participant prior to consenting.

Prior to beginning any study related procedures, the participant will review the informed consent document with a trained staff member. During the informed consent process, the participant will be presented with an optional procedure regarding their electronic communication preference (i.e. receiving communication via an unsecured method such as text, unencrypted email, etc. or via secured method such as in-person consultation, encrypted email, telephone calls, etc.). The consenting staff member will review any questions the patient may have, and confirm that they understand the nature of the research being performed.

**COVID-19 adaptation:** Study staff will review the ICD as detailed above with participants during a virtual “in-person” session, and the ICD will be signed electronically by the participant using an institutionally approved platform.

**Sources of Materials.** Participants will be providing physiological data in the form of saliva and urine (TNE and MA), expired CO, and vitals. Questionnaire data will be obtained that assess previous smoking, smoking cessation history (including Rx medications and NRT's), current and past health and psychiatric conditions, mood, nicotine withdrawal, craving, and cigarettes smoked. All data will be collected specifically for research purposes and will be coded to maintain confidentiality. Relevant medical screening data will be shared with the participant as appropriate for referral and follow-up medical care (see Appendix SS).

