**In-person screening session.** Participants will be instructed to smoke *ad libitum* prior to this session. They will complete basic demographic, health and smoking history questionnaires used in our previous studies that will be reviewed and approved for eligibility by a licensed medical provider. Tobacco product consumption rates will be established using a timeline follow back procedure [95] and smoking history measures used in previous studies [70]. Psychiatric stability, including suicidality criteria, will be assessed using the PHQ-9 [96], a measure of depressive and suicidality symptoms, and the GAD-7 [97], a measure of anxiety symptoms. We will also assess nicotine dependence (Fagerström Test for Nicotine Dependence; FTND) [98] and expired CO. Any individual who is deemed ineligible for study participation for medical/psychiatric reasons will be referred to local medical and/or psychiatric resources. Any participant who spontaneously reports mood, hopelessness, anxiety and/or other symptoms suggesting a persistent change in mood, or who expresses suicidality, will activate the mental health procedures described in Appendix Z.

COVID-19 adaptation: Eligible participants will be scheduled for a virtual “in-person” screening session using an institutionally approved platform, such as Zoom.

**Phase 1: Baseline (week 1).** During this phase, participants will be instructed to smoke their usual brand *ad libitum*.

COVID-19 adaptation: No adaptations needed.

**Phase 2: VLNCC only (weeks 2-4).** During Phase 2, participants will be instructed to smoke only the VLNCCs provided by the study. At the beginning of this phase, they will be given 3 weeks' worth of VLNCCs (150% of their baseline usual brand amount). Regular or menthol will be provided according to their preference. While participants will be asked to use study cigarettes exclusively, they will not be penalized for smoking non-study cigarettes and will be asked to report any such use throughout the study. However, a specific, biochemically verified compensation plan related to VLNCC use will facilitate compliance and honest reporting, as described in the compensation and compliance section below. Smartphone diary assessments as described below will begin during Phase 2. A check-up call may be conducted around 3 days after the start of Phase 2 to troubleshoot any problems the participant may have in terms of starting a new study product. This will allow staff to address any issues that a

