**Financial Compensation for VLNCC compliance.** We know from our U54 that some participants smoked UB cigarettes during the VLNCC condition (~2-3 CPD). However, the effect of non-compliance was negligible, as TNE, our primary measure of nicotine compensation, dropped significantly by week 3 relative to UB smoking (See **Figure 1**). Such would be the case here as well, although in this study we will provide incentives for VLNCC compliance. In our recent unpublished inpatient study, 23 smokers smoked only VLNCC 0.03 mg cigarettes for one week, while 7 others were permitted to "cheat" by allowing them to smoke 1-2 UB cigarettes in addition to the VLNCC's. We determined that a 0.02 nmol/ml cut-off for anatabine (a minor tobacco alkaloid) would identify non-compliance with smoking the 0.03 VLNCC exclusively, by as few as 1-2 UB cigarettes. Anatabine is derived from tobacco and is not affected by e-cig use, whereas TNE is influenced by nicotine from either combustible or non-combustible sources. Thus, anatabine provides an excellent measure of VLNCC compliance. Subjects will be told that compliers (<0.02 nmol anatabine) will receive a \$100 bonus in phases 2 (VLNCC) and 3 & 4 (VLNCC+ECIG). Honest reporters of UB above this level will receive a \$10 bonus, while those above this level who do not report UB use will receive no bonus.

COVID-19 adaptation: No adaptations needed.

**Sample collection and biomarker analyses.** A urine sample (TNE and MA) will be obtained at each visit starting at Visit 1. In addition, participants will be asked to collect a urine sample at home twice a week between appointments, which will be collected at their subsequent appointment. This will allow for better assessment of TNE and MA exposure among low frequency smokers. Smartphones will be used to prompt the participant to obtain the sample. If the participant fails to bring in any/all samples, a deviation will not be logged. A spot urine collection will be conducted during the visit in the event no samples are returned. Urine samples will be sent to the University of Minnesota for analysis. Samples will be de-identified containing only the subject ID generated by the study database, visit number, code corresponding to type of sample, vial number and date collected (example, 456123-03-2-5 9/1/2018).

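### Other tobacco allowed at entry can feed TNE and anatabine but not CPD, and the compliance rule attributes raised anatabine to usual-brand smoking alone

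*Combined protocol and SAP*

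**What the plan says.** **Entry.** Table 3 (section E, Exclusion Criteria) excludes "Self-reported other tobacco use besides cigarettes or little cigars (e.g., hookah, cigarillos, smokeless tobacco, chewing tobacco, pipes, cigars, etc.) on 10 or more days" over the preceding month. Use on up to 9 days is therefore allowed. The only criterion that looks forward over the whole study concerns e-cigarettes: "Unwilling to refrain from other e-cigarette use for the duration of the study, other than what is provided to them for study purposes".

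**On study.** Section D, Procedures, says that in Phase 2 "participants will be instructed to smoke only the VLNCCs provided by the study". The sentence on departures from this is worded for cigarettes: "they will not be penalized for smoking non-study cigarettes and will be asked to report any such use throughout the study". For Phases 3 and 4 participants may mix VLNCCs and the assigned e-cigarette freely, and other tobacco is not mentioned.

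**Outcomes.** CPD, from the daily diary or from the timeline follow-back (TLFB) as back-up, covers VLNCC and usual brand (UB). The note after Table 3 treats little cigars as cigarettes and adds no other product. Section D, Financial Compensation for VLNCC compliance, says that anatabine comes from tobacco and that "TNE is influenced by nicotine from either combustible or non-combustible sources".

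**Compliance rule.** The same paragraph pays $100 below 0.02 nmol/ml anatabine and $10 above it if UB use is reported, "while those above this level who do not report UB use will receive no bonus". The biomarker paragraph likewise presents anatabine as separating VLNCC from UB.

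**Data held.** Section E, Abstinence, says that TLFB also records other forms of tobacco and nicotine. Neither the bonus rule nor the Aim 1 analysis (Statistical Approach) uses that record.

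**The concern.** Aim 1 compares TNE and CPD between the Hi and Lo e-cigarette phases and reads TNE as nicotine compensation with the study products. A cigar or a portion of smokeless tobacco shortly before the analysed urine sample raises TNE with no matching entry in CPD. The reader of the results would then credit the study products with nicotine that came from elsewhere.

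The compliance label has a sharper problem. The rule recognises one explanation for anatabine above the cut-off. A participant who used other tobacco, says so, and truthfully denies UB has no category of their own. As written, they are paid and described like someone who concealed UB smoking. At stake are the meaning of part of the TNE signal and the soundness of statements about VLNCC compliance.

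**Working it through.** **1. Which product reaches which measure** (from the sections above)

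| Source | TNE | Anatabine | CPD | Named in bonus rule |
|---|---|---|---|---|
| Usual brand, little cigars | yes | yes | yes | yes, as UB |
| Study e-cigarette | yes | no | no | not needed |
| Cigars, pipes, hookah, smokeless | yes | can | no | no |

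The last row is the gap. The instruction to smoke only VLNCCs, read literally, covers smoked products in Phase 2. It does not cover smokeless tobacco, and nothing equivalent for other tobacco appears for Phases 3 and 4.

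**2. The bonus rule case by case**

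- Below 0.02 nmol/ml: $100.
- Above, UB reported: $10.
- Above, UB not reported: $0.
- Above, other tobacco reported and UB truthfully denied: no case of its own, so it falls under the third line.

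**3. How often a sample could be affected.** Assumptions not in the documents: use continues at the entry rate, days are independent, and the detection window is 1 to 3 days.

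- Days of use per 21-day phase at the limit: 9/30 × 21 = 6.3.
- Chance that a given sample follows use, at 9 days in 30: 1 − 0.7 = 30% (1 day); 1 − 0.7² = 51% (2 days); 1 − 0.7³ = 66% (3 days).
- At 3 days in 30 with a 3-day window: 1 − 0.9³ = 27%.

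These are chances of recent exposure for one user. They are not effects on TNE, nor the chance of exceeding the cut-off.

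**4. The plan's TNE power, reproduced.** Inputs: Table 1 log(TNE) means and SDs, correlation 0.4, n = 67 per smoker group, alpha 0.05 (taken as two-sided).

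d_z = (m_Lo − m_Hi) / √(s_Hi² + s_Lo² − 2·r·s_Hi·s_Lo)

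- Daily smokers: (2.72 − 3.60) / √(1.28² + 1.62² − 2×0.4×1.28×1.62) = −0.88/1.614 = −0.545. Paired t-test power is 99.3%.
- Intermittent smokers: (2.31 − 3.07) / √(0.80² + 1.29² − 2×0.4×0.80×1.29) = −0.76/1.216 = −0.625. Power is 99.9%.

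Table 2 gives −0.55 and −0.63, each with at least 99%. The figures agree.

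**5. Sensitivity of that contrast.** Assumed: 10-30% of participants are users, and an exposed sample gains 10 to 30 TNE units. For scale, Table 1 anticipates Lo-phase TNE of 33.08 (daily) and 15.88 (intermittent). The gain is added on the raw scale to simulated values and the log is then taken.

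| Scenario | Daily d_z (power) | Intermittent d_z (power) |
|---|---|---|
| No other tobacco | −0.545 (99.3%) | −0.625 (99.9%) |
| 10-30% users, same exposure in both phases (30% or 51% of their samples) | −0.54 to −0.50 (98-99%) | −0.62 to −0.54 (99% or more) |
| 10-30% users, Lo phase only (30% of their samples) | −0.53 to −0.46 (96-99%) | −0.61 to −0.50 (98% or more) |
| Extreme: all are users, Lo phase only, +30 units | −0.29 (66%) | −0.24 (47%) |

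At the worst corner of the 10-30% range (30% users, Lo only, +30), the log difference falls from 0.88 to 0.755 in daily smokers, (0.88 − 0.755)/0.88 = 14%, and from 0.76 to 0.626 in intermittent smokers, (0.76 − 0.626)/0.76 = 18%.

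**The case against.** The strongest reply is that the plan already limits and records this exposure. Phase 2 tells participants to smoke only the study cigarettes, TLFB captures other tobacco, and Hi and Lo are compared within person, blinded and counterbalanced, so stable use mostly dilutes the contrast. The study also models dual use in the natural environment, where some other tobacco is realistic. All of this stands, and it rules out several stronger readings.

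- *Other tobacco is never restricted on study.* Not so: the Phase 2 wording literally covers smoked products. Participant materials not available here may say more.
- *The TNE comparison is underpowered.* Not supported: a serious loss of power appears only in the extreme in which every participant is a user.
- *Use will be higher in the Lo phase and bias the contrast in a known direction.* The documents give no data on this. The direction is also unclear: Table 1 anticipates higher TNE on Hi, so extra Lo-phase nicotine would shrink the difference, whereas the Aim 1 hypothesis predicts lower TNE on Hi, which the same nicotine would appear to support.
- *The $10 payment puts false usual-brand cigarettes into CPD.* This is a possible incentive, not a shown effect. One false report in a phase is 1/21 = 0.05 CPD, against anticipated values of 12.80 and 1.57.
- *Honest users are misclassified in the analysis.* The cut-off was derived for 1-2 UB cigarettes, so how many users of other products exceed it is unknown. Someone who smoked a cigar was indeed not smoking VLNCCs exclusively. The error is in attributing the result to unreported UB. The rule sets payment and interpretation; no analysis set is defined by it.

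What the reply does not answer is that the rule has no place for a truthful report of other tobacco, and that the TLFB record has no stated use in the bonus rule or in Aim 1.

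**Conclusion.** The point holds as a gap in attribution. Other tobacco is allowed on up to 9 days a month at entry. Smokeless tobacco is not covered by the Phase 2 instruction, and the available text restricts no other tobacco in Phases 3 and 4. Such use enters TNE, can raise anatabine, is absent from CPD, and is read as usual-brand smoking by the compliance rule.

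The effect on the Hi v Lo TNE contrast is modest if 10-30% of participants are occasional users: power of about 96% or more, and at worst a shrinkage of roughly 14-18% in the log difference. That range rests on an assumed share of users, assumed TNE gain and assumed window. It should be corrected because the rule gives a wrong attribution as written and the remedy is cheap, not because the primary comparison is at risk.

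**What to change.** 1. Leave the entry criterion unchanged; tightening it is a debatable trade-off for a study of real-world use. Extend the on-study instruction in Phases 2 to 4 so that participants are asked to refrain from, and to report, all non-study tobacco and nicotine products.
2. In Financial Compensation for VLNCC compliance, change the trigger from reporting UB to reporting any non-study tobacco. A truthful report of other tobacco then earns the $10 and is not coded as UB.
3. Use the TLFB record to flag urine samples that follow other-tobacco use within a window fixed in advance. Key the flag to the sample actually analysed: for intermittent smokers the plan (Duration of product exposure) selects the sample closest in time to smoking their median Phase 1 CPD, which need not be the end-of-phase one. Report Aim 1 TNE and the anatabine compliance classification with and without flagged samples. Keep the analysis of all samples as the main one, because removing samples on the basis of on-study behaviour could itself bias the contrast.

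**Cost.** A few more $10 payments, some wording, and one sensitivity analysis on data the plan already collects. Participants who consented before the change would keep the earlier bonus rule, as the Participant Compensation section already provides for previous changes, so the instruction and incentive would differ between cohorts. Step 3 can apply to everyone.
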